4. ANALYSIS SAMPLES

- Screened sample: All participants who undergo screening procedures for purposes of eligibility.
- Randomized sample: All participants who undergo random treatment assignment.
- Safety sample: All participants who undergo random treatment assignment and who receive at least one dose of a study drug.
- Modified intent-to-treat (mITT) sample: All participants who undergo random assignment, who receive at least one dose of both study treatments, and complete the baseline NAC assessment.
- Per protocol (PP) sample: All participants in the mITT sample for whom the primary endpoint is assessed and who are compliant with study treatment, defined as taking at least 50% of SLIT or SLIT placebo tablets and at least 75% of dupilumab or dupilumab placebo injections throughout the treatment period. See [Section 7.3](#) for the formula to calculate treatment compliance for each study treatment; for SLIT or SLIT placebo, the primary method of calculating observed doses taken will be used for PP sample determination.

If a participant is administered the incorrect treatment, analyses based on the randomized, mITT, and PP samples will be based on the treatment arm to which they were randomized. Whereas analyses based on the safety sample will be based on the treatment arm associated with the medication they actually received, regardless of their random assignment.

For purposes of grouping participants into the treatment arm they actually received, the following rules apply:

- Participants randomized to double-placebo arm that received at least one dose of SLIT and at least one dose of dupilumab will be considered in the combination of SLIT and dupilumab arm.
 - Also, in the rare eventuality that a participant randomized to double-placebo arm receives zero doses of SLIT and at least one dose of dupilumab, then the actual treatment will be the combination of SLIT and dupilumab arm.
- Participants randomized to double-placebo arm that received at least one dose of SLIT and zero doses of dupilumab will be considered in the SLIT plus dupilumab placebo arm.
- Participants randomized to SLIT plus dupilumab placebo arm that received at least one dose of dupilumab will be considered in the combination of SLIT and dupilumab arm.
- Participants randomized to combination of SLIT and dupilumab arm will be considered in this arm, unless they received 100% placebo doses for both treatments, in which cases they will be considered in the double-placebo arm; or if they received all dupilumab placebo doses but some SLIT treatment, in which cases they will be considered in the SLIT plus dupilumab placebo arm.
- Otherwise, actual treatment arm will be set to the randomized treatment arm

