7.2 PROHIBITED MEDICATIONS

Use of the following medications is prohibited during study participation:

- Administration of live attenuated vaccines: live attenuated vaccines should not be given concurrently with dupilumab as clinical safety and efficacy has not been established (if needed, live vaccine should be administered to participants before commencement of dupilumab). These vaccines should not be given within 4 weeks of dupilumab or dupilumab placebo injection.
- Tricyclic antidepressants
- Monoamine oxidase inhibitors
- Anti-IgE, anti-IL-5, anti-IL-5 receptor, other monoclonal antibodies targeting the human immune system, or any other biologic therapies. Antiviral monoclonal antibodies are permitted.
- Refer to Appendix 7 for required medication washout periods prior to the NAC and skin prick testing

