8.3.3 CLINICAL ASSESSMENTS

Clinical allergy assessments comprise NACs and several forms of skin testing and provide eligibility information, clinical characterization and allergy status. It is important that prior to all such assessments, participants avoid medications that might unduly modify allergic responses independent of the study interventions. Certain procedures may generate aerosols and will be conducted only if they comply with local hospital guidelines at the time of the procedure. Washout periods for specific medications are shown in Appendix 7.

Potential aerosol generating procedures

- Nasal Allergen Challenge
- Visual Analogue Scale (Appendix 9)
- Peak expiratory flow testing
- Peak nasal inspiratory flow testing
- Pulmonary Function Testing (Spirometry, FEV₁)

Non-aerosol generating procedures

- Skin prick test endpoint titration – *Phleum pratense*
- Intradermal skin test – *Phleum pratense*
- Skin prick test panel: Timothy grass pollen (*Phleum pratense*), silver birch (*Betula verrucosa*), mugwort (*Artemisia vulgaris*), house dust mite (*Dermatophagoides pteronyssinus*), cat hair (*Felis domesticus*), dog hair (*Canis familiaris*), *Aspergillus fumigatus*, *Cladosporium herbarum*, *Alternaria alternata*, negative control, and positive control (*histamine dihydrochloride*)

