APPENDIX 7. MEDICATION WASHOUT PERIODS

Medication Washout Periods Before Nasal Allergen Challenge and Intradermal Tests	
Medications	Time
Oral β-agonists	
Conventional release (e.g., Salbutamol, Ventolin)	12 hours
Modified release (e.g., Bricanyl)	2 days
Leukotriene modifiers (e.g., Montelukast, Singulair, Zafirlukast, Accolate)	3 days
Oral steroid (e.g., prednisone, prednisolone)	14 days
Theophylline product	14 days
Short-acting preparation (e.g., Nuelin SA, Slo-Phyllin, Aminophylline)	24 hours
Long-acting preparation (e.g., Uniphyllin Continus, Phyllocintin Continus)	2 days
Certain antihypertensive medications (Beta-blockers, Calcium channel inhibitors)	2 days
Rhinitis Medications	Time
Sodium Cromoglicate (e.g., Rynacrom, Vividrin)	7 days
Antihistamines (e.g., Cetirizine, Desloratadine, Neoclaritin, Fexofenadine, Telfast, Levocetirizine, Xyzal, Loratadine, Chlorphenamine, Piriton, Atarax, Zaditen)	5 days
Decongestants (e.g., pseudoephedrine, phenylephrine)	3 days
Antihistamine-decongestant tablets/liquids (e.g., Zyrtec D, Claritin-D)	5 days
Nasal corticosteroids (e.g., Flixonase NS, Flixonase Nasules, Nasonex, Nasacort, Fluticasone Propionate, Nasonex, Beclomethasone, Beconase, Betnesol, Vista-Methasone, Budesonide, Rhinocort Aqua)	14 days

[figure not shown]

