7.3. Measurement of Treatment Compliance

Treatment compliance will be summarized by treatment arm through the total duration of study treatment (104 weeks). In each of the treatment arms, compliance rate will be calculated using the following formula:

$$\text{Compliance (\%)} = \frac{\text{observed doses taken}}{\text{expected number of doses}} \times 100$$

The observed doses taken for each study treatment will be calculated as follows:

- SLIT and SLIT placebo: participants were asked to return used SLIT and SLIT placebo blister packs and unused tablets at each study visit. The number of empty blisters was collected, along with a participant-reported quantity taken and a reliability grade for the participant-reported quantity recorded. The observed doses taken will be calculated in two ways:

- Primary method: the total sum of a) the participant-reported quantity taken if the reliability grade = “reliable” plus b) the number of empty blisters returned if the reliability grade of the participant-reported quantity is not “reliable”, across all dispensing/return visits
- Supportive method: the total sum of number of empty blisters returned, across all dispensing/return visits
- Dupilumab and dupilumab placebo: the total sum of injection records where injection date is non-missing

The expected number of doses for each study treatment are as follows:

- SLIT and SLIT placebo: planned to be taken once per day for 104 weeks, which means:
 - *Expected number of doses* = 104 weeks × 7 days per week = 728 doses
- Dupilumab and dupilumab placebo: planned initial subcutaneous injection of 600mg (counted as two doses) at Week 0 followed by a single injection of 300mg every two weeks after for remaining 104 weeks, which means:
 - *Expected number of doses* = $2 + \left(\frac{104}{2}\right) = 54$ doses

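### The per-protocol sample keeps participants who received another arm's treatment and counts them as compliant under their randomised arm

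*SAP*

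**What the plan says.** SAP section 4 defines the PP sample as "All participants in the mITT sample for whom the primary endpoint is assessed and who are compliant with study treatment", with compliance "defined as taking at least 50% of SLIT or SLIT placebo tablets and at least 75% of dupilumab or dupilumab placebo injections". Protocol 13.3.1 gives the same definition.

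SAP section 4 then covers participants given the wrong product: "analyses based on the randomized, mITT, and PP samples will be based on the treatment arm to which they were randomized". Only the safety sample is grouped by treatment received. The grouping rules for that sample foresee a combination-arm participant whose doses of both products were all placebo. For safety that person moves to the double-placebo arm. For PP, nothing moves or removes them.

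SAP 7.3 counts injections as "the total sum of injection records where injection date is non-missing". It counts tablets from participant reports or returned empty blisters. Neither count looks at which product was given.

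SAP 9.1.4 repeats the primary model on the PP sample. The sensitivity analyses in SAP 9.1.3 deal with missing data only.

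On washout, Protocol 7.2 says: "Refer to Appendix 7 for required medication washout periods prior to the NAC and skin prick testing". Protocol 8.3.3 asks that, before these tests, "participants avoid medications that might unduly modify allergic responses independent of the study interventions". Neither PP definition mentions washout, and SAP 7.1 only lists and counts protocol deviations.

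**The concern.** The mITT analysis follows a treatment-policy estimand (SAP section 5) and rightly keeps everyone as randomised. The PP analysis is there to answer a different question: what happens in participants who took what they were assigned. On wrong treatment it does not do so. Someone who took every dose of another arm's regimen passes both thresholds and is analysed in an arm whose regimen they did not receive.

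mITT and PP then share the same contamination, so agreement between them says little about whether wrong-treatment cases influenced the result. A secondary gap is that a challenge done inside an Appendix 7 washout period counts fully in PP, whether it supplies the baseline covariate or the year-3 endpoint.

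**Working it through.** **Inputs** (Protocol 13.6): placebo mean 3.81; SD 1.53, 1.64 or 1.73; 30 evaluable per arm; two-sided alpha 0.05; 80% power; stated detectable reduction 29% to 33%. From SAP 7.3: 728 expected tablets and 54 expected injections.

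**The plan's own figure.** Detectable difference = (1.960 + 0.842) × SD × √(2/30).

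- SD 1.53: 1.107, and 1.107/3.81 = 29.05%
- SD 1.64: 1.186, and 1.186/3.81 = 31.1%
- SD 1.73: 1.251, and 1.251/3.81 = 32.85%

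This reproduces 29% to 33%.

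**What PP entry requires.** 0.50 × 728 = 364 tablets. 0.75 × 54 = 40.5, so 41 injections. Active and placebo doses both count, so a participant with every dose from the wrong arm is 100% compliant.

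**Dilution per full crossover.** A 30% effect is 0.30 × 3.81 = 1.143. One of 30 double-placebo participants who received the whole active regimen, and responded to it fully, lowers that arm's mean by 1.143/30 = 0.038, which is 0.038/1.143 = 3.3% of the effect. One combination participant who received only placebo costs the same. Partial exposure would be expected to cost less.

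**Keeping against excluding.** Suppose m of 30 combination participants received only placebo and responded as placebo. The values of m are assumptions; the documents give no count. SD is 1.64 and the true reduction 31%. The observed reduction if they are kept is 31% × (1 − m/30). Power is by normal approximation.

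| m | Reduction if kept | Power if kept | Power if excluded (31% retained) |
|---|---|---|---|
| 0 | 31.0% | 0.797 | 0.797 |
| 1 | 30.0% | 0.769 | 0.790 |
| 2 | 28.9% | 0.740 | 0.783 |
| 3 | 27.9% | 0.709 | 0.775 |

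At m = 3, the other SDs give 26.1% kept against 29% excluded (SD 1.53; power 0.711 against 0.777), and 29.7% against 33% (SD 1.73; power 0.717 against 0.782).

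**Washout: direction only.** A year-3 challenge blunted by medication narrows the difference if it falls in the placebo arm and widens it if it falls in the combination arm. A blunted baseline challenge acts through the covariate. With the usual positive coefficient, a lowered baseline in the placebo arm raises that arm's adjusted year-3 mean and widens the difference. The net direction depends on arm and visit. The documents give nothing from which to compute a size.

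**The case against.** The protocol and SAP give the same PP definition, and an adherence-and-completer sample is a recognised choice. That stands: a reader might infer that the two documents conflict, or that the sample is not per protocol at all, and neither follows. The sample does screen on dose counts and on having the endpoint. The defect is that the dose counts ignore product.

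A reader might also infer that the SAP expects wrong-treatment cases because it writes rules for them. It does not say so, and it describes one branch as rare. Those rules can also be triggered by a single dose, so a reclassified participant need not be a full crossover, and 3.3% is close to a ceiling per case at a 30% effect.

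Dilution does not normally manufacture a positive superiority result, and PP is only supportive. The listing of randomised and actual treatment (SAP 7.2) would show cases to readers. All of this limits the importance of the point, but none of it makes PP answer its own question.

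On washout, a reader might infer that the plan knowingly retains breached challenges and that these shrink the effect by a calculable amount. The documents support neither. The retention is an omission, not a stated rule. Rescue medication is supplied around the pollen season (Protocol 7.1) while challenges run from September to January (Protocol 8.5). No breach is documented, and the direction varies as shown above.

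**Conclusion.** The point holds for wrong treatment, where it rests on an explicit sentence in SAP section 4 and on product-blind counting in SAP 7.3. The size is about 3.3% of a 30% effect per full crossover between the two primary arms. This assumes 30 evaluable per arm and that the participant responds entirely as the arm whose treatment was received. The number of cases is unknown and may be zero. The primary mITT analysis does not change, so this is a minor improvement to a supportive analysis. The washout gap is a secondary addition with unknown direction and no stated size.

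**What to change.** In SAP section 4 and Protocol 13.3.1:

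1. Count only doses of the assigned product towards the existing 50% and 75% thresholds.
2. Exclude from PP any participant whose actual treatment differs from the randomised arm beyond a pre-set dose threshold. Step 1 alone is not enough: a double-placebo participant with 41 placebo injections could still have had 54 − 41 = 13 active ones. A zero-tolerance rule would be too strict, since it would remove someone for one wrong tablet in 728 while 50% adherence is accepted.
3. Remove PP from the as-randomised sentence.
4. As a secondary addition, exclude participants with a documented Appendix 7 washout breach before the baseline or year-3 challenge.

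Product identity is held by the unblinded pharmacist (Protocol 3.5), so an unblinded party without access to outcome data should identify wrong-product cases. Washout breaches should be judged blind from concomitant-medication dates.

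The note at the end of the SAP postdates database lock. If the data are already unblinded, report the revised sample as a labelled post hoc sensitivity analysis, with counts of each type of case by arm.

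The cost is SAP and protocol wording and a review of records already planned for collection. PP may lose a few participants; mITT loses none.

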5.2.3 COMBINATION THERAPY

There is no available data concerning the concurrent administration of Grazax® and Dupixent® in man. Both agents are well-tolerated with a defined profile of generally mild AEs, in particular mild-moderate, largely self-resolving reactions at the site of local administration for both products and the occurrence of mild-moderate conjunctivitis for Dupixent®, so far largely confined to participants with atopic eczema. The mechanism of action of Dupixent® is such that it is anticipated that the local allergy-related side-effects of sublingual Grazax® will likely be ameliorated by Dupixent®.

Grazax® will be administered sublingually daily and Dupixent® will be administered by subcutaneous injection every 2 weeks. On the day that Dupixent® is administered, this will be separated from Grazax® by a minimum interval of 6 hours. This duration was chosen because any reactions to Grazax® occur within 1 hour thereby allowing for attribution of any AEs to the appropriate study therapy.

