13.3 ANALYSIS PLAN

13.3.1 ANALYSIS SAMPLES

Screened sample: All participants who undergo screening procedures for purposes of eligibility.

Randomized sample: All participants who undergo random assignment. Participants will be analyzed according to the treatment arm to which they were randomized, regardless of the treatment they actually received.

Safety sample: All participants who undergo random assignment and who receive at least one dose of a study drug. Participants in the safety sample will be analyzed with the arm associated with the medication they actually received, regardless of their random assignment.

Modified intent-to-treat (mITT) sample: All participants who undergo random assignment, who receive at least one dose of both study medications, and complete the baseline NAC assessment (See Appendix 1 and 2). Participants will be analyzed according to the treatment arm to which they were randomized, regardless of the treatment they actually received.

Per protocol (PP) sample: All participants in the mITT sample for whom the primary endpoint is assessed and who are compliant with study treatment, defined as taking at least 50% of SLIT or SLIT placebo tablets and at least 75% of dupilumab or dupilumab placebo injections throughout the treatment period.

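### Two actual-treatment rules for the safety sample do not follow the medication received: an all-placebo SLIT-arm participant stays in the SLIT arm, and dupilumab-only exposure is counted as the combination

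*SAP*

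**What the plan says.** Protocol Section 13.3.1 sets the principle: "Participants in the safety sample will be analyzed with the arm associated with the medication they actually received". SAP Section 4 repeats it: "analyses based on the safety sample will be based on the treatment arm associated with the medication they actually received". The SAP then lists rules for deciding which arm was actually received.

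- **Randomized to double-placebo.** At least one dose of each active product leads to the combination arm. Dupilumab without SLIT is treated separately: "in the rare eventuality that a participant randomized to double-placebo arm receives zero doses of SLIT and at least one dose of dupilumab". Such a person is also counted under the combination. SLIT without dupilumab ("Participants randomized to double-placebo arm that received at least one dose of SLIT and zero doses of dupilumab") leads to the SLIT plus dupilumab placebo arm.
- **Randomized to SLIT plus dupilumab placebo.** There is one rule: "Participants randomized to SLIT plus dupilumab placebo arm that received at least one dose of dupilumab will be considered in the combination" arm.
- **Randomized to the combination.** They stay there unless every dose of both products was placebo (then double-placebo), or every dupilumab dose was placebo but some SLIT was taken (then the SLIT arm).
- **Everyone else.** "Otherwise, actual treatment arm will be set to the randomized treatment arm".

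SAP Section 10.3 builds the treatment-emergent adverse event (AE) tables on the safety sample by treatment arm, so these rules decide which column a person's events enter. The randomized, modified intent-to-treat and per-protocol samples are analysed as randomized.

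**The concern.** An as-received rule should put people with the same exposure in the same column, whatever arm they were randomized to. It should also not describe someone as exposed to a product they never took. The listed rules fail the first test for all-placebo exposure and the second for dupilumab-only exposure.

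What is at stake is the labelling of the AE columns. Protocol Section 5.2.3 says of the two products together: "There is no available data concerning the concurrent administration". The combination column is therefore the trial's most novel safety result. A reader will take everyone in it to have had both products, and everyone in the SLIT column to have had SLIT. Nothing in Section 4 asks for a footnote where that is untrue.

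**Working it through.** **Inputs.** The assignment rules are in SAP Section 4, the planned arm size of 36 in Protocol Section 3.1, and the expected doses in SAP Section 7.3.

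**The plan's own dose figures reproduce.** SLIT: 104 × 7 = 728 tablets. Dupilumab: 2 + 104/2 = 54 doses.

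**Tracing the rules.** There are four possible patterns of active exposure and three randomized arms, so 12 cases. Each cell shows the arm SAP Section 4 assigns.

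| Active product received | Randomized double-placebo | Randomized SLIT | Randomized combination | Matches what was received? |
|---|---|---|---|---|
| Neither | Double-placebo | **SLIT** | Double-placebo | Not for the SLIT arm |
| SLIT only | SLIT | SLIT | SLIT | Yes |
| Both | Combination | Combination | Combination | Yes |
| Dupilumab only | **Combination** | **Combination** | **Combination** | No; no such arm exists |

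Eight of the 12 cases agree with a simple rule that any active dose counts as exposure. Four do not.

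1. *Neither product, randomized to SLIT.* The only trigger listed for this arm is a dupilumab dose. With none, the default applies and the person is tabulated as SLIT-exposed. The same exposure in a combination-arm participant has an explicit rule and goes to double-placebo. The column thus depends on the randomized arm, which is what an as-received analysis is meant to avoid.
2. *Dupilumab only, from any arm.* For double-placebo the placement is written out. For SLIT, the trigger is a dupilumab dose with no condition that SLIT was taken. For the combination, both exits require that all dupilumab doses were placebo, so a person with some dupilumab and no SLIT stays.

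**Size per person.** One participant in a planned arm is 1/36 = 2.8%. If moved into an arm that already holds 36, the share is 1/37 = 2.7%.

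**Would the other outputs show it?** Only in part. Compliance under SAP Section 7.3 counts dated injections and tablets taken without separating active from placebo, and SAP Section 10.2 plans no other exposure summary. SAP Section 7.2 lists randomized arm beside actual treatment. If actual treatment there is the arm derived under Section 4, an all-placebo SLIT-arm participant would show no discrepancy.

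**When can the cases arise?** Mainly when the wrong product is dispensed. One narrow route needs no error. Protocol Section 8.5 gives the first injection at Visit 0 and the first tablet at least 12 hours later, and the safety sample needs a dose of only one study drug. Someone who stopped between the two would be in the safety sample without having taken SLIT.

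**The case against.** **Dupilumab-only placement is partly forced.** The trial has no dupilumab-only arm, so any of the three columns is imperfect. The SAP foresees the case for double-placebo participants, calls it rare and fixes the rule in advance. Leaving such a person in double-placebo would put dupilumab exposure in the comparator. This stands against moving them to another arm. It does not stand against marking them.

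**A reader might infer that moving a participant on one wrong dose is itself a fault.** One dupilumab dose is 1/54 = 1.9% of those planned and one tablet is 1/728 = 0.14%, yet all of that person's treatment-emergent events move. The documents do not make this an error. Counting any active dose as exposure is a common safety convention, and it keeps reactions to an accidental active dose out of the placebo column. The asymmetry follows from it: one placebo dose does not undo exposure. Assignment by majority of doses would be no improvement. A combination participant with 26 active injections of 54 would count as unexposed to dupilumab, a double-placebo participant who reacted to one active injection would stay under placebo, and 27 of 54 is a tie.

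**Listings exist.** SAP Section 7.1 lists deviations with type, date and reason, and Section 10.1 lists all safety data. A careful reader could reconstruct recorded dispensing errors from these. That limits the harm, but the summary tables would still carry the wrong label.

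**Errors should be few.** Under Protocol Section 3.5 an unblinded pharmacist matches kits to the assignment. This too stands, and it bears on size rather than on whether the rules are right.

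**Conclusion.** The point holds as a minor one. The missing all-placebo rule for the SLIT arm is a plain omission: the plan states a principle, applies it to the combination arm and not to the SLIT arm. The dupilumab-only placement departs from the same principle, but it is a compromise forced by the design and needs disclosure rather than reversal.

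The scope is narrow. Only safety-sample summaries are touched; primary and secondary efficacy results are not. Nothing changes unless a participant received the wrong product or, more narrowly, stopped after the first injection and before the first tablet. The documents do not say whether either happened. If it did, each person is about 2.8% of a planned arm.

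A reader might infer that these rules make the combination look safer. The documents do not establish that. They give no dispensing-error rate and no AE pattern for such participants. A person moved because of a reaction to a wrong active dose would raise the combination percentages. A SLIT-arm participant moved after a dupilumab dose would normally bring SLIT exposure, with local side effects reported in 46–61% (Protocol Section 1.2.1). Protocol Section 5.2.3 expects dupilumab to lessen those effects, so such a person could raise local reaction rates in the combination column. Dilution by people who never took SLIT is also possible, so the direction is open.

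**What to change.** 1. In SAP Section 4, add the mirror rule: a participant randomized to SLIT plus dupilumab placebo who received only placebo for both treatments is counted in the double-placebo arm. State whether this covers someone who had the placebo injection and no tablet.
2. For any participant with no SLIT and at least one dupilumab dose, whatever the randomized arm, add a footnote to the combination column or show them in a separate row or listing.
3. Leave the one-dose trigger as it is.

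The cost is a line or two of SAP text and one derivation from dosing and dispensing records. The note attached to the SAP shows that the plan is final and the database locked, so this would now be a post-lock change. It could be recorded in a short note of the kind already used for the AUC formula. If no participant's arm changes and none had dupilumab only, a sentence saying so in the clinical study report closes the matter.
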